5. GENERAL METHODOLOGY AND CONVENTIONS

5.1. Hypotheses and Decision Rules

There are no hypotheses and decision rules defined for the study. A descriptive estimation approach will be used to assess all study objectives in the study.

Point estimates and nominal 95% CIs will be provided for all safety and immunogenicity endpoints at each planned analysis.

No formal multiplicity adjustments will be applied due to multiple endpoints or multiple looks for the same endpoint.

5.2. General Methods

CIs for all endpoints in the statistical analysis will be presented as 2-sided at the 95% level unless specified otherwise.

5.2.1. Analyses for Binary Endpoints

Descriptive statistics for binary variables (eg, proportions) are the percentage (%), the numerator (n) and the denominator (N) used in the percentage calculation, and the 95% CIs where applicable.

The exact 95% CI for binary endpoints for each group will be computed using the F distribution (Clopper-Pearson)¹ and implemented in SAS PROC FREQ.

The 95% CI for the between-group difference for binary endpoints will be calculated using the Miettinen and Nurminen² method.

5.2.2. Analyses for Continuous Endpoints

5.2.2.1. Geometric Mean Titers

The GMTs will be calculated as the mean of the assay results after making the logarithm transformation and then exponentiating the mean to express results on the original scale. Two-sided 95% CIs will be obtained by taking log transforms of assay results, calculating the 95% CI with reference to the Student t distribution, and then exponentiating the confidence limits.

5.2.2.2. Geometric Mean Fold Rises

GMFRs are defined as ratios of the results after vaccination to the results before vaccination. GMFRs are limited to participants with nonmissing values at both time points.

GMFRs will be calculated as the mean of the difference of logarithmically transformed assay results (later time point minus earlier time point) and exponentiating the mean. The associated 2-sided 95% CIs will be obtained by constructing CIs using the Student t distribution for the mean difference on the logarithm scale and exponentiating the confidence limits.

5.2.2.3. Geometric Mean Ratios

The GMR will be calculated as the mean of the difference of logarithmically transformed assay results and exponentiating the mean. Two-sided CIs will be obtained by calculating CIs using the Student t distribution for the mean difference of the logarithmically transformed assay results and exponentiating the confidence limits.

5.2.2.4. Reverse Cumulative Distribution Curves

Empirical RCDCs will plot proportions of participants with values equal to or exceeding a specified assay value versus the indicated assay value, for all observed assay values. Data points will be joined by a step function with the line first going down and then to the right to the next assay value.

5.3. Methods to Manage Missing Data

5.3.1. Safety Data

Standard algorithms for handling missing AE dates, missing AE severity, missing laboratory test values, and missing ECG values will be applied according to the Pfizer safety rules. Missing data handling rules on the safety data are described in detail in the corresponding endpoint sections.

5.3.1.1. Reactogenicity Data

Completely missing reactogenicity e-diary data will not be imputed.

For derived variables based on reactogenicity data, if any day of the 7-day e-diary is available, the "any day (Day 1 through 7)" data will be considered nonmissing.

The reactogenicity data are collected through the reactogenicity e-diary, which does not allow participants to skip the question. Therefore, for a specific day, if the e-diary data are transferred for that day, all the reactogenicity data for the participant on that day are nonmissing. No missing reactogenicity data will be imputed other than what is described in Section 3.1.1 and Section 3.1.2.

In summary, for any participant with all 7 days of the e-diary missing, this will not be included in the analysis (ie, assuming MCAR). If only 1 to 6 days of e-diary data are transferred, the reactogenicity data for the missing day(s) are considered as answering "no" for all reactions. This is based on the common assumption that no reports mean no events.

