8.3.5. Electronic Diary

All participants will be required to complete a reactogenicity e-diary after each vaccination given at Visits 1 and 201 through an application installed on a provisioned device or on the participant's own personal device. All participants will be asked to monitor and record local reactions, systemic events, and use of antipyretic medication for 7 days from the day of administration of the study intervention given at Visits 1 and 201. The reactogenicity e-diary allows recording of these assessments only within a fixed time window, thus providing the accurate representation of the participant's experience at that time. Data on local reactions and systemic events reported in the reactogenicity e-diary will be transferred electronically to a third-party vendor, where they will be available for review by investigators and the Pfizer clinicians at all times via an internet-based portal.

At intervals agreed to by the vendor and Pfizer, these data will be transferred electronically into Pfizer's database for analysis and reporting. These data do not need to be reported by the investigator in the CRF, unless the participant missed an e-diary entry and the participant experienced a prompted local reaction or systemic event, in which case any missed entries should be included in the AE CRF.

Investigators (or designee) will be required to review the reactogenicity e-diary data online at frequent intervals as part of the ongoing safety review.

The investigator or designee must obtain stop dates from the participant for any ongoing local reactions, systemic events, or use of antipyretic medication on the last day that the reactogenicity e-diary was completed. The stop dates should be documented in the source documents and the information entered in the CRF.

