9.3.1. General Considerations

CIs for all endpoints in the statistical analysis will be presented as 2-sided at the 95% level unless specified otherwise.

The safety analyses are based on the safety population. Participants will be summarized by vaccine group according to the study interventions they actually received. Completely missing reactogenicity e-diary data will not be imputed; missing AE dates will be handled according to the Pfizer safety rules. Missing e-diary data not recorded in the e-diary will be recorded on the AE CRF. Therefore, the primary analysis will use reactogenicity recorded as AEs in the CRF to impute the missing e-diary data.

For all the immunogenicity endpoints, the analysis will be based on the evaluable immunogenicity population. Antibody titers below the LLOQ or denoted as BLQ will be set to 0.5 × LLOQ for immunogenicity analysis. No other missing assay data will be imputed in the analyses. All immunogenicity analyses will be performed after the imputation of the antibody concentrations or antibody titers that are below the LLOQ.

An additional analysis may be performed based on the mITT immunogenicity population if there is a large enough difference in sample size between the mITT immunogenicity population and the evaluable immunogenicity population. Participants will be summarized according to the vaccine group to which they were randomized. Missing serology data will not be imputed.

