10.11.9.3.1. General Considerations for Substudy A

Refer to Section 9 for general considerations of statistical analyses.

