1. VERSION HISTORY

Table 1. Summary of Changes

Version/ Date	Associated Protocol Amendment	Rationale	Specific Changes
1 03 Nov 2022	1 18 Oct 2022	N/A	N/A
2 19 Jan 2023	2 09 Dec 2022	Update to match protocol amendment 2	 Updated throughout to reflect the addition of a new age stratum and the removal of 22/23 specific HAI strains Updated Table 3 and Table 4 to reflect that redness/swelling <2 cm is not considered a reaction Updated Section 4 to specify how participants enrolled at multiple sites will be handled in the outputs Updated Section 6.3.2 with more details about the C4591044 data Updated Section 6.4 with details about subgroup analyses by SARS-CoV-2 status at baseline

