2.1. Modifications to the Analysis Plan Described in the Protocol

This document may modify the plans outlined in the protocol; however, any major modifications of the primary endpoint definitions or their analyses will also be reflected in a protocol amendment.

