Presence of any local reaction.	The reaction is reported as "yes" with a diameter of >2.0 cm for redness/swelling or "yes" for pain any day from Day 1 through Day 7.	For all 3 local reactions, participant reports "no" (or "yes" with a diameter ≤2.0 cm for redness/swelling) on all 7 days (Day 1 through Day 7) or as a combination of "no" (or "yes" with a diameter ≤2.0 cm for redness/swelling) and missing on all 7 days. (Day 1 through Day 7).	Participant does not report any data for all 3 local reactions on all 7 days (Day 1 through Day 7).

a. The variables will be derived for any of the local reactions (redness, swelling, and pain at the injection site) and for any of the severe local reactions within the interval from Day 1 through Day 7 after vaccination.

Severity and Maximum Severity

Redness and swelling will be measured and recorded in measuring device units (range: 1 to 21) and then categorized during analysis as absent, mild, moderate, severe, or potentially life-threatening based on the grading scale in Table 5. Measuring device units can be converted to centimeters according to the following formula: 1 measuring device unit = 0.5 cm. Pain at the injection site will be assessed by the participant as absent, mild, moderate, or severe according to the grading scale in Table 5.

Mild Moderate Severe Potentially (Grade 1) Life-Threatening (Grade 2) (Grade 3) (Grade 4) Pain at the Does not interfere Prevents daily Emergency room Interferes with injection site with activity. activity. activity. visit or hospitalization for severe pain. Redness >2.0 cm to 5.0 cm >5.0 cm to 10.0 cm >10 cm Necrosis or (11 to 20 measuring exfoliative

device units).

device units).

>5.0 cm to 10.0 cm

(11 to 20 measuring

(≥21 measuring

(≥21 measuring

device units).

device units).

>10 cm

dermatitis.

Necrosis.

Table 5. Local Reaction Grading Scale

(5 to 10 measuring

>2.0 cm to 5.0 cm

(5 to 10 measuring

device units).

device units).

Swelling

For each local reaction, the maximum severity grade will be derived for the e-diary collection period (Day 1 through Day 7, where Day 1 is the day of each vaccination) as follows:

maximum severity grade = highest grade (maximum severity) within 7 days after vaccination (Day 1 through Day 7) among severity grades where the answers are neither "no" nor missing for at least 1 day during the interval from Day 1 through Day 7.

Duration of Each Local Reaction (First to Last Day Reported)

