6. ANALYSES AND SUMMARIES

6.1. Primary Endpoints

6.1.1. Local Reactions and Systemic Events

6.1.1.1. Main Analysis

- Estimand strategy: Treatment policy (Section 2.2.1).
- Analysis set: Safety population (Section 4).
- Analysis methodology: 95% CI of the proportion of participants reporting each event, using the Clopper-Pearson method (Section 5.2.1).
- Intercurrent events and missing data: The participants without any e-diary data
 throughout the 7 days after vaccination will be excluded from the analysis at that
 vaccination; for participants who discontinue, all collected data will be included;
 intermediate missing values will not be imputed. Partially missing e-diary data are
 imputed as "no" (Section 5.3.1.1); e-diary data that are confirmed as errors will not be
 used for analysis.

- Analysis timing: Day 1 through Day 7 after vaccination.
- Reporting results:
 - O Descriptive statistics, including the proportion (%), the numerator (n) and the denominator (N) used in the proportion calculation, and the 95% CI for percentage using the Clopper-Pearson method, will be presented for each study intervention group and overall, for participants 18 through 64 years of age and ≥65 years of age separately and combined.
 - O Bar charts with the proportions of participants for each and any local reaction, and each and any systemic event, through the 7 days following vaccination will be plotted for each study intervention group and overall. The bars will be divided into severity categories to highlight the proportions of participants by maximum severity, for participants 18 through 64 years of age and ≥65 years of age separately and combined.

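### For missed e-diary days in Substudy A, protocol 9.3.1 fills in from the AE CRF but the Substudy A SAP scores the day 'no'; the two primary reactogenicity rules need to be reconciled

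*SAP*

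**What the plan says.** **Protocol, current version (Amendment 6).** Section 9.3.1 leaves wholly missing diaries unimputed and says that missed entries go on the AE CRF. It continues: "Therefore, the primary analysis will use reactogenicity recorded as AEs in the CRF to impute the missing e-diary data". Nothing in 9.3.1 limits this to Substudy B. Section 10.11.9.3.1 carries it into Substudy A: "Refer to Section 9 for general considerations of statistical analyses". The Substudy A primary-analysis table (10.11.9.3.2) contains no override. On data collection, Section 8.3.5 covers the diary started at Visit 1, which is Substudy A, as well as Visit 201. When a participant missed an entry and had a prompted reaction, it directs: "in which case any missed entries should be included in the AE CRF".

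**Substudy A SAP, version 2.** Section 5.3.1.1 excludes participants with all 7 days missing. For the rest: "If only 1 to 6 days of e-diary data are transferred, the reactogenicity data for the missing day(s) are considered as answering" 'no' for every reaction. It allows no imputation beyond Sections 3.1.1 and 3.1.2. Those sections use the CRF only for the end date of an unresolved reaction. Tables 3 and 4 score any mixture of 'no' and missing days as absent, and count redness or swelling as present only when reported "with a diameter of >2.0 cm for redness/swelling". Section 6.1.1.1 repeats the rule: "Partially missing e-diary data are" set to 'no'.

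**Status of the SAP.** Its version history gives 19 January 2023 and the reason "Update to match protocol amendment 2". Section 2.1 reserves a general right: "This document may modify the plans outlined in the protocol". It lists no departure on this point.

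**The concern.** Local reactions and systemic events are primary safety endpoints in Substudy A. Take a participant who sent some diary days, missed others, and has a reaction from a missed day recorded on the AE CRF. The protocol counts that reaction and the SAP scores the same day 'no'. A programmer cannot follow both texts, and a reader of the report cannot tell which rule produced the rates.

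The SAP justifies its rule by the assumption that an absent report means no event. Under protocol 8.3.5 a report may exist, in another part of the database. Substudy A and Substudy B rates would also be derived differently under one master protocol without either text saying so. Both documents exclude wholly missing diaries, and that is not in question.

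**Working it through.** The plan states no figure for this, so the check is a comparison of texts followed by a small calculation.

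**1. Does the protocol rule reach Substudy A?** Yes, as written. Section 9.3.1 is general, 10.11.9.3.1 invokes it, and 10.11.9.3.2 does not displace it. The rule is repeated for Substudy B in 10.12.9.1.1.1 and is not repeated in the Substudy A appendix, so the intended scope is unclear.

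**2. Two hypothetical participants, each with a partly transmitted diary**

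| Case | Diary | AE CRF | Protocol 9.3.1 | Substudy A SAP |
|---|---|---|---|---|
| 1 | 'no' on all days sent; Days 2-3 missed | injection-site pain, onset Day 2 | present | absent |
| 2 | mild pain Day 1; Day 2 missed | severe pain, Day 2 | present, maximum severe | present, maximum mild |

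Case 1 lowers presence under the SAP. It arises only if every day with that reaction was missed. Case 2 leaves presence unchanged but puts one more participant in the SAP's mild category and one fewer in severe. So the SAP's presence rate is equal to or below the protocol-rule rate, while a single maximum-severity category can be higher or lower.

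**3. Dates** (the amendment log is used here for dating only)
- Amendment 2: 09 December 2022. Substudy A SAP v2: 19 January 2023.
- Sponsor's internal committee reviews of Substudy A safety data: March and May 2023 (protocol 2.1). These reviews draw on at least 4 weeks of follow-up (10.11.4.1), and the diary lasts 7 days.
- Amendment 5: 15 August 2023. Its log shows edits to 8.3.5 and 9.3.1, and names missed diary data on the AE CRF as an analysis change for Substudy B.
- Substudy B SAP v2: 22 February 2024. It contains the AE CRF step (3.1.1, 5.3).

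The likeliest reading is that the Substudy A SAP predates the AE CRF wording and was not updated.

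**4. Size per affected participant.** Inputs are about 30 per group per age stratum, 180 per stratum and 360 in all (protocol 10.11.9.5 and 10.11.4.1).
- Group of 30: 1/30 = 3.3 points.
- Both ages combined, 60: 1/60 = 1.7 points.
- Age stratum, 180: 1/180 = 0.6 points.
- All participants, 360: 1/360 = 0.3 points.

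**5. Effect on the planned interval.** Clopper-Pearson limits for x of n are the 2.5% point of Beta(x, n−x+1) and the 97.5% point of Beta(x+1, n−x).
- Rare event: 0/30 = 0% (upper limit 1 − 0.025^(1/30) = 11.6%) against 1/30 = 3.3% (0.1 to 17.2%).
- Common event: 17/30 = 56.7% (37.4 to 74.5%) against 18/30 = 60.0% (40.6 to 77.3%). The half-width of the latter is (77.3 − 40.6)/2, or about 18 points, so one participant is small beside it.

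The documents give no e-diary missingness and no count of reactions held only on the AE CRF. The number of affected participants therefore cannot be derived, and with none the shift is zero.

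**The case against.** The strongest defence is that the protocol hands this question to the SAP. Sections 9.3 and 10.11.9.3 say that the SAP will set out the handling of missing data, and both documents let the SAP modify the protocol. The SAP has an explicit rule with a stated reason. A SAP dated January 2023 could not declare a departure from wording that probably arrived in August 2023. This stands as an explanation: a reader might infer that the SAP was wrong when written, or that the sponsor set a protocol rule aside, and the documents support neither. It does not make the two current rules agree.

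A second defence is that the protocol sentence was meant for Substudy B. The restatement in 10.12.9.1.1.1, the amendment log and the Substudy B SAP all point that way, and Substudy A diary periods were probably over before Amendment 5. This is suggestive, not proven. The Substudy A stopping rules (10.11.8.6) refer to prompted reactions recorded either in the diary or as AEs, so AE CRF records of this kind were at least foreseen. If Substudy B alone was meant, 9.3.1 should say so.

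A third defence is that little is lost. The substudy is descriptive, without hypotheses, and an event on the AE CRF stays in the AE, severe-AE and SOC/PT summaries (SAP 6.1.2). That stands and limits the severity.

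**Conclusion.** The mismatch is certain as a matter of text. Its numerical effect is unknown and may be zero. It falls between minor and should-fix: it touches a primary safety endpoint and costs little to repair, but the analysis is descriptive.

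Three stronger readings are tempting and are not supported:
- That all SAP reactogenicity figures are equal or lower. This holds for presence only (case 2 above).
- That a missed-day reaction would go unreported. One record can decide whether an event appears in the reactogenicity table, as with 0/30 against 1/30, but it remains in the AE tables.
- That Substudy A rates are understated by some estimable amount. The documents give no basis for a figure.

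The conclusion assumes that 9.3.1 applies to Substudy A as written. Whether AE CRF capture of missed entries was in place while Substudy A diaries were open is not shown, and the remedy depends on it.

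**What to change.** First check whether the Substudy A AE CRF holds reactogenicity events with onset on Days 1 to 7.

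**If it does**, amend Substudy A SAP 2.2.1 (data source), 3.1.1, 3.1.2, 5.3.1.1 and 6.1.1.1. For participants with any e-diary data, consolidate the AE CRF events first, then score the remaining missing days 'no', as Substudy B SAP 3.1.1 and 5.3 do. The SAP should also state:
- that local reactions count at the right-arm site only, since Group 6 receives QIV in the left arm;
- how AE intensity maps to diary grades;
- how redness or swelling without a measurement is treated, given the diary threshold of more than 2.0 cm;
- whether 'related', as used in Substudy B SAP 3.1.1, means causally related. Protocol 9.3.1 has no causality limit, so adding one would be a departure to declare;
- whether consolidated events also stay in the main AE rate.

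Keep the diary-only rates as a sensitivity analysis. Label the change as made after sponsor data review, because the substudy is open-label, the sponsor is unblinded and safety data were reviewed in March and May 2023.

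**If it does not**, limit the 9.3.1 sentence to Substudy B. State in the Substudy A SAP and report that reactogenicity rates are diary-only and may be understated.

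The first route costs SAP wording, a derivation already drafted for Substudy B and the extra rules above; presence rates may rise slightly. The second costs one scope sentence in the protocol and one caveat in the SAP and report. Neither needs new data or participants.

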3.1.3. Use of Antipyretic Medication

The use of antipyretic medication is also recorded in the e-diary from Day 1 through Day 7, where Day 1 is the day of vaccination. For the use of antipyretic medication from Day 1 through Day 7 after vaccination, the following endpoints and variables will be derived for analysis following the same rules as for local reactions (see Section 3.1.1), where applicable.

- Presence (yes or no) of use of antipyretic medication on each day (Day 1 through Day 7).
- Presence (yes or no) of use of antipyretic medication on any day (Day 1 through Day 7).

Page 19 of 40

- Duration (first to last day reported) of use of antipyretic medication.
- Onset day of use of antipyretic medication.

The use of antipyretic medication will be summarized and included in the systemic event summary tables but will not be considered a systemic event.

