6.1.1.2. Sensitivity/Supplementary Analyses

To support the assessment of reactogenicity, the endpoints below, as specified in Section 3.1.1 and Section 3.1.2, will be summarized with the same analysis time point and analysis population:

- Duration (days) of each local reaction and each systemic event after vaccination.
- Onset day of each local reaction and each systemic event after vaccination.
- Presence of each and any severe local reaction and each and any severe systemic event, on each of the 7 days and for "any day (Day 1 through Day 7)."

The presentation of the results will include a basic descriptive summary without 95% CIs (Section 5.2.1).

These continuous endpoints will be summarized by displaying the n, mean, median, standard deviation, minimum, and maximum for each study intervention group and overall, for participants 18 through 64 years of age and ≥65 years of age separately and combined.

In addition, the proportions of participants reporting prompted local reactions and systemic events, by maximum severity level, with any e-diary errors will be included as a supplemental summary for participants 18 through 64 years of age and ≥65 years of age separately and combined.

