6.5.2.3. E-Diaries

The participants who were vaccinated and who transmitted and completed e-diaries will be summarized according to the vaccine actually received, for participants 18 through 64 years of age and ≥65 years of age separately and combined. Besides the analysis described in Section 3.4.2, the summary will also include the number and percentage of vaccinated participants not transmitting the e-diary, transmitting the e-diary, and completing the e-diary for any day in the required reporting period, by assigned study intervention and age group.

The number and percentage of participants transmitting and completing the e-diary for each day in the required reporting period, and overall, will be tabulated for each study intervention group and for the total sample, for participants 18 through 64 years of age and ≥65 years of age separately and combined.

The safety population will be used.

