The onset day of each local reaction or systemic event will be derived. Onset day is defined as the first day of reporting the reaction or event with any severity after study intervention administration. For a reaction or event collected in multiple sources, the earliest reported date of the reaction will be used in calculating the onset day.

Presence will be derived for each day and any day.

Use of Antipyretic/Pain Medication

The use of antipyretic/pain medication is also recorded in the e-diary from Day 1 through Day 7, where Day 1 is the day of vaccination. For the use of antipyretic/pain medication from Day 1 through Day 7, the following endpoint and variable will be derived:

• Presence (yes or no) of use of antipyretic/pain medication after vaccination (on any day and for each day).

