5.3. Methods to Manage Missing Data

Standard algorithms on handling missing AE dates will be applied according to Pfizer safety rules. A completely missing start date for an AE is not allowed in data collection. For derived variables based on reactogenicity data, if any day of the 7-day e-diary is available, the "any day (Day 1 through Day 7)" data will be considered nonmissing. It is expected that these reactogenicity events would be queried by the investigator for the missing e-diary days and would be entered in the AE CRF if any reactogenicity was not reported in the e-diary due to missed days. Therefore, the primary analysis will use the reactogenicity recorded in the AE CRF to impute the partially missing e-diary data to estimate the reactogenicity rate during the e-diary collection period. The AE CRF is designed as a log page, which means only events that occurred will be recorded and events that did not occur will not be recorded. Therefore, all remaining missing days are considered as having answered "no." This imputation can reasonably estimate the reactogenicity event rates during the e-diary collection period.

Antibody titers below the LLOQ, denoted as BLQ, or below the LOD will be set to $0.5 \times \text{LLOQ}$ for GMT analysis. No other missing assay data will be imputed in the analyses.

When calculating a fold rise, the assay results will be converted to $0.5 \times LLOQ$ if assay results are < LLOQ, except when the prevaccination assay result is < LLOQ while the postvaccination result is $\ge LLOQ$, in which case the prevaccination value will be set to LLOQ. If both the numerator and denominator are < LLOQ, then both will be converted in the same way.

Values for sera that are insufficient, indeterminate results, or values recorded as "not done" will be set to "missing."

LLOQs for each assay used in this study will be included in serology data transfer once they are available.

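### Substudy A: scoring untransferred e-diary days as 'no' scales each by-day severe-reaction rate down by that day's diary completion, and the SAP lacks the protocol's AE-CRF step

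*SAP*

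**What the plan says.** The Substudy A SAP deals with missed diary days in section 5.3.1.1. For a participant with some days but not all: "If only 1 to 6 days of e-diary data are transferred, the reactogenicity data for the missing day(s) are considered as answering" 'no' to every reaction. The stated ground is: "This is based on the common assumption that no reports mean no events". An entirely empty diary is treated differently: "for any participant with all 7 days of the e-diary missing, this will not be included in the analysis", on a missing-completely-at-random assumption. The same section explains that questions cannot be skipped, so a transferred day has no missing items.

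Daily variables are derived for severe or Grade 4 local reactions (3.1.1), severe systemic events (3.1.2) and antipyretic use (3.1.3, following the local-reaction rules where applicable). Section 6.1.1.2 plans a summary of "Presence of each and any severe local reaction and each and any severe systemic event, on each of the 7 days" as well as over the whole week. It is descriptive and carries no confidence intervals. No section states a denominator for a single day. Section 6.5.2.3 does tabulate "The number and percentage of participants transmitting and completing the e-diary for each day in the required reporting period".

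The current protocol goes further. Section 8.3.5 sends a prompted reaction on a missed day to the AE CRF. Section 9.3.1, which 10.11.9.3.1 applies to Substudy A, has the primary analysis use those records to fill missing diary data.

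**The concern.** For the any-day endpoint one report in the week is enough, so treating a missed day as 'no' is a tolerable, disclosed convention. For a single day, no other day can make up for the gap. The numerator can come only from those who reported that day, while the denominator appears to be everyone with at least one diary day. The diary accepts entries only within a fixed window (protocol 8.3.5), so a missed day cannot be completed later.

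The by-day table is where a reader looks to see when severe reactions peak and how quickly they go. If completion falls over the week, loss of entries looks like resolution. If completion is worse in one group, that group looks better tolerated. Safety and tolerability are the primary objective, so these tables will be read even though they are supplementary.

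**Working it through.** No sample size, power or stated rate rests on this rule, so the plan has no figure to reproduce.

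**Inputs**
- Group size: about 30 per vaccine group per age stratum (protocol 10.11.9.5).
- Daily completion c among participants with at least one diary day: not given; assumed 60% to 100%.
- True daily severe rate p: not given; assumed 3%, 10% and 20%.
- Share k of missed-day severe reactions recovered from the AE CRF: 0 under the Substudy A SAP; above 0 if the protocol step is used.
- Missing days are assumed unrelated to reactions.

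**Formula.** Of N participants, N × c report and contribute N × c × p events. The other N × (1 − c) are scored 'no' except for the recovered share. So reported rate = p × [c + (1 − c) × k].

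**Step 1, k = 0.** The reported rate is p × c, and the relative loss is 1 − c at any true rate:

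| Completion that day | True 3% | True 10% | True 20% |
|---|---|---|---|
| 95% | 2.85% | 9.5% | 19.0% |
| 90% | 2.7% | 9.0% | 18.0% |
| 80% | 2.4% | 8.0% | 16.0% |
| 70% | 2.1% | 7.0% | 14.0% |
| 60% | 1.8% | 6.0% | 12.0% |

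**Step 2, slope.** With a flat true 10% and completion falling linearly from 100% to 70%, Days 1 to 7 print as 10.0, 9.5, 9.0, 8.5, 8.0, 7.5 and 7.0%. Completion constant at 80% prints 8.0% every day: lower, but with no slope.

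**Step 3, groups.** Two groups with the same true 10%, one at 90% completion and one at 70%, print as 9.0% and 7.0%.

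**Step 4, shape.** A true rate rising from 2% to 10%, with completion falling from 100% to 70%, still rises, from 2.0% to 7.0%. A true profile of 2, 10, 5, 2, 1, 0.5, 0.5% still peaks on Day 2 (9.5%).

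**Step 5, one group of 30.** Two severe reports among 20 reporters are 2/20 = 10.0% (Clopper-Pearson 95% CI 1.2 to 31.7). Under the 'no' rule they print as 2/30 = 6.7% (0.8 to 22.1).

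**Step 6, AE-CRF recovery.** At a true 10% and 70% completion, k = 0.5 gives 10% × (0.70 + 0.30 × 0.5) = 8.5%; k = 1 gives 10.0%.

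**Texts side by side.** One bullet in SAP 6.1.1.1 says that intermediate missing values are left unimputed; its next sentence sets partly missing diary data to 'no'. Protocol 9.3.1 fills missed days from the AE CRF. SAP 5.3.1.1 rules out imputation beyond what 3.1.1 and 3.1.2 describe, and neither of those mentions the AE CRF. The SAP version history ties this SAP to protocol amendment 2; the current protocol is amendment 6.

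**The case against.** **The daily denominator is inferred.** Section 5.3.1.1 points back to 3.1.1 and 3.1.2, and Tables 3 and 4 there combine 'no' with missing only for presence over the seven-day interval. Read that way, the daily variables are not imputed at all. This reading is open, but the closing sentences of 5.3.1.1 apply the rule to missing days without limiting it to the any-day variable, and 6.1.1.1 points both ways. A programmer could produce either table, so the text needs settling.

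**The size depends on why days are missed.** If symptom-free participants are the ones who skip, the 'no' rule is right and a reporters-only denominator overstates: 3 events in 30 with 9 non-reactors skipping becomes 3/21 = 14.3% instead of 10%. This stands as a real downside. Conversely, if people skip because they feel worse, the loss exceeds the table above and a reporters-only denominator corrects only part of it.

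**Other safeguards exist.** AE-CRF recovery would shrink the loss, participants are told to contact the site at once about severe reactions, and onset day and duration have their own summaries. All true. But the Substudy A SAP has no step that brings AE-CRF events into the diary analysis. The amendment history lists the AE-CRF wording for 8.3.5 under Amendment 5 (15 August 2023), after the sponsor's review committee had reviewed Substudy A safety data for both age groups in March and May 2023. Recovery may therefore be limited in practice; the documents do not say. Missed antipyretic entries are not recovered at all, since 8.3.5 covers only reactions and systemic events.

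**The stakes are modest.** With 30 per group, 10% against 8% is 3.0 against 2.4 participants. Daily completion is tabulated, so an alert reader could notice a drop.

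**Conclusion.** The point holds for Substudy A. As the SAP is most naturally read, each by-day severe rate is scaled by that day's completion, a relative loss of 10%, 20% or 30% at 90%, 80% or 70% completion. These sizes rest on assumed completion and on missing days being unrelated to reactions. The affected output is supplementary and has no confidence intervals. The missing AE-CRF step and the contradiction in 6.1.1.1 are wording faults that hold whatever completion turns out to be.

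Three stronger readings are tempting and are not supported:
- *Every missed day becomes 'no'.* Participants with all seven days missing leave the analysis.
- *The profile falls whatever the vaccine does.* The effect is proportional: constant completion adds no slope, and a rising or peaked true profile keeps its direction or peak in the examples worked above.
- *Substudy B has the same fault.* Its SAP does say "Presence will be derived for each day and any day", and "Therefore, all remaining missing days are considered as having answered" 'no', but only after AE-CRF reactogenicity has been used (5.3). Its reporting section (6.1.1.2) summarises presence and severe events for any day, not day by day.

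**What to change.** In the Substudy A SAP:
1. In 5.3.1.1, limit the rule that a missed day counts as 'no' to the any-day (Day 1 through Day 7) variable.
2. In 6.1.1.2, and for any by-day antipyretic summary, use as denominator the participants whose diary was transferred for that day, and print n/N for each day.
3. In 5.3.1.1 and 6.1.1.1, align the any-day analysis with protocol 9.3.1 by using AE-CRF reactogenicity for missed diary days, and delete the sentence saying that intermediate missing values are not imputed.

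Do not extend the by-day denominator to participants who have only an AE-CRF record, in either substudy. The Substudy B SAP describes the AE CRF as a log of events that occurred, so this would add only people with events. With 100 participants and a true rate of 10%, suppose 80 report (8 events) and both events among the other 20 are recovered: the present Substudy B rule gives 10/100 = 10.0%, while the extended denominator gives 10/82 = 12.2%.

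The cost is SAP wording, a denominator change in the by-day programs and an AE-CRF merge for the any-day analysis; tables already produced would need re-running. No new data are needed for the by-day change, because daily transmission is already tabulated. The price is a smaller N on later days (21 of 30 at 70% completion) and rates that may be somewhat high if symptom-free participants are the ones who skip entries. Printing n/N lets the reader judge that.
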